32.0 Study Methods

32.1 Provide a description of how the study question (hypothesis) will be tested and how participants or their health information will be involved in the study.

For help with this question please click on the help button.

Study Design: This will be a randomized, controlled study comparing a clinical pharmacist-led disease management intervention by the Clinical Pharmacy Cardiac Risk Service (CPCRS) to usual care (UC). Randomization will be 1:1 and will occur at the patient-level.

Patient Selection Criteria

Inclusion Criteria:

All active KPCO non-institutionalized patients from the Denver/Boulder metropolitan area with a validated non-cardioembolic ischemic stroke diagnosis within the past 5 years who:

- § Are ≥ 18 years of age at the time of informed consent, and
- § Are Eligible for CPCRS enrollment, and

§ Have uncontrolled blood pressure (the most recent value >130/80 mmHg noted in the medical record), and/or

§ Have last LDL-C, within the previous 365 days, that is ≥ 100 mg/dL (the most recent will be used).

Exclusion Criteria:

Patients will be excluded if:

§ → >85 years of age at the time of consent,

§ Have transient ischemic attacks, subarachnoid hemorrhage, intracerebral hemorrhage, or cardioembolic stroke as their only validated stroke history,

§ Die within 30 days of stroke,

§ Are already followed by the Clinical Pharmacy Cardiac Risk Service (CPCRS). These patients either have a history of coronary artery disease (acute MI, CABG, percutaneous coronary interventions, and/or coronary catheterizations), are at high-risk for CAD as determined by the cardiologist, or have peripheral arterial disease,

§ Have a diagnosis of dementia or a terminal illness in which the life expectancy is <3 years per the discretion of the primary care provider,

§ Have notation in the medical record of memory issues or other conditions which, based on the judgment of study staff, suggest that the patient may not be able to provide informed consent,

§ Are pregnant or breast-feeding, or

§ Do not consent to participate

§ Currently listed on the "Do Not Call List"

Both English and Spanish speaking patients will be eligible for participation.

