Patient Screening for Eligibility: All patients with ICD-9 codes 430.XX to 438.XX (estimated to be approximately 15,000 patients at KPCO) will be administratively identified from KPCO claims databases starting January 1, 2000 and administratively pulled into a HealthTrac®-Stroke registry. Each patient included in the registry will undergo a validation process to ensure stroke type and event dates are accurate (Appendix I). This validation process will be similar to that used for the HealthTrac®-CAD registry already used by CPCRS.

Data collection

The HealthTrac-Stroke® registry, electronic medical record and KPCO administrative, claims, pharmacy, and laboratory data will be used for data collection and documentation of study group assignments. Patient characteristics to be collected at baseline (within 6-months of enrollment date) include demographics (age, sex, race (at time of enrollment), co-morbidities (hypertension, cardiac disease history, atrial fibrillation, diabetes mellitus, depression, sleep apnea, smoking status [current, past (quit \geq 5 years ago), never]. Cardiovascular-related medications and dosages will be identified from administrative KPCO medication databases. These medications will include lipid-lowering medications, antihypertensive medications, (diuretics, β -blockers, ACE inhibitors/angiotensin receptor blockers, calcium channel blockers, and others), antiplatelet agents (i.e., aspirin, clopidogrel, ticlopidine, dipyridamole/ASA, prasugrel). Laboratory data will be extracted from the KPCO laboratory results administrative database. The number and type of encounters (clinic, procedure, hospital, emergency room, clinical documentation, email, telephone, etc) over the study period will be collected for both groups.

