33.0 Data Analysis

33.1 Describe the data analysis plan for this study. For help with this question please click on the help button.

STUDY Outcome Measures

The outcome measures selected for the study are based on AHA/ASA guidelines for prevention of stroke in patients with ischemic stroke or transient ischemic attack.^{19,20} The surrogate measures to be evaluated are the "ABCs" which include Antiplatelet/antithrombotic therapy, Blood pressure control, Cholesterol control, and Smoking cessation. These variables will be evaluated at various time points during the study in part to evaluate the CPCRS processes of care for attaining surrogate measures in the short-term and maintenance of these outcomes long-term compared to Usual Care. Surrogate outcome measures will be evaluated at 1 and 3 years after randomization.

Primary Outcome Measure

The primary outcome will be the proportion of patients in each group who attain recommended LDL-C and BP goals 3 years after randomization. Patients in both groups will be mailed reminder letters within 60 days of their study end date to have their fasting lipid profile drawn or blood pressure measured, as necessary. If patients do not have the necessary values obtained within 30 days of their study end date, they will be mailed a second reminder letter. In the event,

patients still do have the required laboratories and/or blood pressure values, patients will be called by the study staff.

The LDL-C goal will be <100 mg/dL for all patients as recommended by clinical practice guidelines.^{19,20} The proportion of patients with an LDL-C <70 mg/dL in each group will also be reported. A fasting lipid profile dated \pm 60 days of the study end date will be utilized for study outcome assessment. In the event that a fasting lipid profile is not or can not be obtained, a non-fasting lipid panel, if available, will be utilized for study outcome assessment. However, all attempts will be made to obtain a fasting lipid profile for study purposes.

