For the primary outcome of proportion at both BP and LDL-c goals at year 3, and based on prior studies,²⁸ we estimate that 45% of patients in the Usual Care group will meet the end point at 3-years and conservatively estimate that 60% the CPCRS intervention will meet the end point. An enrollment number of 173 patients per group will be required, with a two-sided alpha of 0.05 and power of 80%. To account for about a 20% dropout rate, the number will be inflated to 200 patients per group.

It is estimated that approximately 5200 patients will have validated stroke, of which

4200 will have ischemic stroke (both cardioembolic and non-cardioembolic and approximately 2500 will have non-cardioembolic ischemic stroke. We anticipate that with this pool of patients, we should be able to meet this sample size calculation.

Statistical Analysis

All statistical analyses will be performed on an intention-to-treat basis utilizing SAS (SAS, Cary, NC) statistical software. Baseline subject characteristics for each study group will be reported as means, medians, and standard deviations for interval- and ratio-level variables (e.g., age, length of time between events, mean lipid levels) and percentages for nominal- and ordinal-level data (e.g., sex, cardiovascular event history). All patients who completed follow-up in their randomized intervention assignment at years 1 and years 3 (as outlined in outcomes assessment) will be included regardless of whether they interacted with CPCRS or not. Interval-level outcome variables will be assessed for normality of their distributions and appropriate tests (e.g., t-test, rank-sum test) will be used to assess differences in mean values between groups. Study outcomes will be dichotomized as yes/no (e.g., reached BP & LDL goal levels yes/no, persistent

with lipid-lowering therapy yes/no). To assess differences in proportions between groups on dichotomous outcome variables, Pearson's chi-square test of association will be utilized. An alpha < 0.05 will be considered statistically significant.

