The study team is requesting an alteration of written informed consent for this study. The CPCRS conducts the majority of their clinical care via telephone and do not have routine face-to-face contact with patients. Therefore, the study team is asking for approval for telephone consent (Appendix III) and requesting a waiver of HIPAA from the IRB. All study staff have completed the required research training.

A waiver of HIPAA Authorization is also being requested to analyze data in aggregate for all non-participants (those who are eligible and those who refuse to participate). A limited data set for these patients will be created so that we may characterize the initial pull of eligible study patients with those who do and do not agree to be contacted for study participation. The following data will be collected administratively: age, sex, co-morbidities, and current antihyperlipidemic and antihypertensive medications.

Once patients have consented to participate in the study, they will be randomized in 1:1 fashion at the patient-level to the Intervention (i.e. CPCRS care) or Usual Care groups using a pre-determined computer-generated list of random numbers. The randomization scheme will be stored in a separate electronic file, stored behind KPCO's firewall. Patients will be notified of the treatment group they have been assigned to. For patients in the CPCRS arm, study personnel will notify the CPCRS supervisor of the patients study enrollment and the supervisors will enroll the patient into CPCRS using standard procedures as for other patients.

Study participation for patients in both groups will be documented in the Problem List of HealthConnect. The note will include that patients are enrolled in a clinical trial, the arm to which they are randomized and contact information in case there are questions related to the study.

7. Study Procedures:

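### The primary endpoint is tested by an unadjusted chi-square; prespecified adjustment for the baseline BP and LDL-C already read at eligibility may add power, by an amount the protocol does not let us pin down

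*Protocol*

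**What the plan says.** **Endpoint.** Protocol section 33.0: "The primary outcome will be the proportion of patients in each group who attain recommended LDL-C and BP goals 3 years after randomization". The goals are LDL-C below 100 mg/dL and BP below 130/80 mmHg, and a patient counts as a success only if both are met.

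**Test.** Section 33.0, Statistical Analysis, turns the endpoint into yes/no and states that Pearson's "chi-square test of association will be utilized". No covariate or stratum is named.

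**Entry.** Section 32.0 admits patients whose most recent BP is above 130/80 mmHg and/or who meet the lipid criterion: "Have last LDL-C, within the previous 365 days, that is ≥ 100 mg/dL (the most recent will be used". This gives three routes: BP only, LDL-C only, or both.

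**Allocation.** Section 45.3 says patients are "randomized in 1:1 fashion at the patient-level" from a computer-generated list. It mentions no stratification by entry route.

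**Sample size.** Section 33.0: "we estimate that 45% of patients in the Usual Care group will meet the end point at 3-years", and the investigators "conservatively estimate that 60% the CPCRS intervention will meet the end point". That gives 173 per group at two-sided 0.05 and 80% power, raised to 200 for about 20% dropout. Patients who completed follow-up are analysed.

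**The concern.** The entry criteria are nearly the complement of the endpoint. A patient admitted on one route, with the other value known to be controlled, starts with one of the two components met. A patient admitted on both routes starts with neither. It is reasonable to expect these patients to differ in their chance of having both at goal three years later, and the values that separate them are read before randomisation.

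As written, neither the stated allocation nor the analysis uses this information. Chance differences between arms in the mix of routes therefore add noise to the unadjusted difference. Precision that costs no extra patients may be left unused.

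**Working it through.** **1. Reproduce the plan's figure.** Inputs from section 33.0: p0 = 0.45, p1 = 0.60, two-sided alpha 0.05, power 80%. The pooled mean is 0.525.

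n = [1.960·√(2·0.525·0.475) + 0.842·√(0.45·0.55 + 0.60·0.40)]² / 0.15² = (1.384 + 0.588)² / 0.0225 = 172.8, so **173 per group**. This matches exactly, and it is the formula for the unadjusted comparison.

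**2. Power of the chi-square at other sizes.** Power = Φ[(0.15·√n − 1.384)/0.698].
- n = 173: 80.0%
- n = 200 (no dropout): (2.121 − 1.384)/0.698 = 1.056, so 85.4%
- n = 160 (200 × 0.80): (1.897 − 1.384)/0.698 = 0.735, so 76.9%

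The last figure follows from the inflation: 173/0.80 = 216.25, so 217 would be needed, not 200.

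**3. What stratifying by route would add.** The protocol gives neither the share of patients per route nor goal rates by route, so both are assumed. In each scenario the overall rates were held at 45% and 60%, with a common odds ratio across routes. The chi-square was compared with a Cochran-Mantel-Haenszel (CMH) test stratified by route, in 40,000 simulated trials per scenario (Monte Carlo error about √(0.77·0.23/40,000) = 0.2 points). R² is the share of Usual Care outcome variance that route explains. Assumed shares (BP only/LDL-C only/both) are 50/20/30%, or 40/30/30% in the last row. Entries are power in %, chi-square to CMH.

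| Usual Care rates by route | R² | n = 160 | n = 173 | n = 200 |
|---|---|---|---|---|
| Weak: 50/45/37% | 0.013 | 77.2 to 77.5 | 79.2 to 80.2 | 85.6 to 85.8 |
| Moderate: 54/49/26% | 0.061 | 76.7 to 79.1 | 79.2 to 82.5 | 85.6 to 87.5 |
| Strong: 60/55/14% | 0.167 | 76.9 to 84.6 | 79.3 to 87.6 | 85.6 to 91.6 |
| Very strong: 64/59/6% | 0.271 | 77.0 to 90.7 | 79.2 to 92.9 | 85.7 to 95.8 |

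At 160 per arm the gain is 0.3 points (weak), 2.4 (moderate) and 7.7 (strong). Over the three sizes the strong case gives 6.0 to 8.3 points. Simulated type I error was 0.045 to 0.050 for the chi-square and 0.049 to 0.051 for CMH. At 173 the chi-square ran slightly conservative (0.045 to 0.048), so a small part of the gain in that column reflects its level.

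**4. A second simulation with logistic adjustment.** n = 160, assumed shares 40/20/40%, 3,000 trials per scenario (Monte Carlo error about 0.8 points), unadjusted to adjusted:
- rates 50/50/37.5%: 76.7 to 77.3%
- rates 55/55/30%: 77.2 to 79.5%
- rates 60/60/22.5%: 76.1 to 82.5%
- rates 55/55/30% plus a moderate continuous baseline predictor: 77.9 to 82.8%

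The pattern is the same, and no scenario in either simulation lost power.

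**5. Break-even.** Treat adjustment as raising the effective n to n/(1 − R²). Power of 80% at 160 per arm then needs 160/(1 − R²) = 172.8, so R² = 1 − 160/172.8 = 0.074. As a check, R² = 0.05 gives 79.0% and R² = 0.10 gives 81.1%.

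**6. Chance imbalance.** If 40% enter on both routes (assumed), the between-arm difference in that share at 160 per arm has SE √(2·0.4·0.6/160) = 5.5 points, with 95% limits of about ±10.7. Multiplied by goal-rate gaps of 25 points (55 against 30) to 37.5 points (60 against 22.5), this shifts the unadjusted difference by up to about ±2.7 to ±4.0 points, against a target of 15.

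**The case against.** The strongest reply is that nothing here is wrong. The trial is sized for an unadjusted comparison and analysed by one. The test holds its level, and chance imbalance is already covered by its error rate. **This stands.** The shifts in step 6 are random error and not bias.

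A second reply is that covariate adjustment is often left to the SAP, which is not shown. This stands in part. The protocol does not leave the choice open: it names the test. If an SAP already names an adjusted primary analysis, the two documents only need aligning.

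Some stronger readings are tempting but unsupported:
- **The chi-square loses power against the plan, or causes the shortfall below 80%.** It does not. It delivers 80.0% at 173, and the 76.9% at 160 comes from the dropout inflation. Adjustment may offset that shortfall but does not correct it.
- **The routes have very different chances of success.** A difference is plausible from the definitions, but the protocol gives no rates. Entry status rests on the most recent readings and the outcome lies three years on, so the spread could be weak and the gain close to nil.
- **Randomisation is known to be simple.** The protocol states no stratification by route, but it does not say whether the list is blocked or stratified.
- **The six-month baseline window discards older LDL-C values that made patients eligible.** The phrase "Patient characteristics to be collected at baseline (within 6-months of enrollment date" introduces demographics, comorbidities and smoking. Laboratory data come in a later sentence with no window, and eligibility allows 365 days for LDL-C.
- **Adjustment is free.** LDL-C is not required of patients who qualify on BP. One without a value cannot be placed in the BP-only or the both group, so a three-route indicator would be missing for exactly those patients. Logistic adjustment also targets a conditional odds ratio unless the result is standardised.

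**Conclusion.** The point holds as an efficiency improvement. The planned test and the 173 per group agree with each other and are valid. What the plan forgoes is the use of baseline values that bear directly on the endpoint and are already in hand.

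At 160 per arm the expected gain is about 0 to 3 points of power for a weak to moderate spread and about 8 for a strong one (6 to 8 over 160 to 200 per arm), with type I error held at about 5%. Larger gains, of 10 to 14 points, appear only under an extreme spread that nothing in the protocol supports.

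These figures rest on assumed route shares and goal rates, and on every patient being classifiable by route. They describe the CMH test and the logistic Wald test, not the standardised risk difference itself, so they indicate scale and do not predict.

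**What to change.** Before outcomes are seen, name one primary model in section 33.0:
- **Model:** logistic regression with arm, baseline SBP and DBP as read at the eligibility review, and LDL-C status from the same review in three levels: below 100 mg/dL, 100 mg/dL or more, no value within 365 days. The third level keeps BP qualifiers without an LDL-C in the same model as everyone else.
- **Estimate:** the standardised (marginal) risk difference with 95% CI, so the result stays on the scale of the 45% against 60% planning assumption.
- **Support:** keep the Pearson chi-square as a supportive analysis.

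The change is to wording only and needs no new data. The downside is slightly more analysis work and a not-measured LDL-C category that carries less information for some BP qualifiers. The dropout inflation should be dealt with on its own.

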34.0 Risks and Benefits

34.1 Provide justification for the risks and benefits of this study. For help with this question please click on the help button.

THE ADDITIONAL DISCOMFORT FROM STUDY PROCEDURES WILL BE REASONABLE IN RELATION TO SOC. WHILE THE BENEFIT TO AN INDIVIDUAL PATIENT IS UNKNOWN AT THIS TIME, THE RISKS ARE NEGLIGIBLE AND THE INFORMATION GAINED WILL PROVIDE IMPORTANT INSIGHT. THEREFORE, WE CONCLUDE THAT RISK: BENEFIT IS REASONABLE FOR THIS STUDY.

35.0 Study Type

35.1 Please identify what type of research study this is:

- Data Only
- Enrollment
- Both/Other

36.0 Enrollment

36.1 Estimated number of participants:

Within KPCO:

400

Total all sites:

400

Comments:

36.2 Will non-Kaiser Permanente members be enrolled in this study at KPCO?

Yes No

Comments:

36.3 Does this study use an investigational DRUG or DEVICE?

- Investigational Drug
- Investigational Device
- Neither

37.0 Enrollment

37.1 Check the participant documents that will be used in this study:

- Consent Form(s)
- Authorization Form
- Surveys/Questionnaires
- Contact/Recruitment Letter
- Post Cards
- Recruitment Flyer
- Phone scripts
- Other (Please list below)

37.2 Please list the other participant documents:

Reminder letters

37.3 Please list the study documents that have not been developed yet.

38.0 Enrollment

38.1 Special study procedures: Select all that may apply.

These procedures should be explained clearly in the Informed Consent , if applicable.

- Tissue collection for research testing (Includes blood and bodily fluids)
- Tissue/specimen banking for future testing
- Genetic testing
- HIV testing
- Gene therapy
- Videos, audiotapes, or photographs taken of study participants
- Other
- Not applicable

Other special study procedures:

39.0 Informed Consent Questionnaire

39.1 What type of approval are you requesting? (Select all that apply)

- Approval of draft consent/assent forms attached to this application
- A waiver of informed consent
- An alteration of informed consent
- A waiver of signed informed consent

40.0 Informed Consent Questionnaire

40.1 Does the proposed research present no more than minimal risk to the study participants? Yes No**40.2 Could there be any legal or psychosocial risk to the study participants?** Yes No**40.3 Explain how the waiver or alteration of informed consent will not adversely affect the rights and welfare of participants.**

The study team is requesting an alteration of written informed consent for this study. The CPCRS conducts the majority of their clinical care via telephone and do not have routine face-to-face contact with patients. During the telephone consent process, patients will be asked specific questions concerning study activities to verify comprehension and autonomy. The patient will have time to discuss participation with family and friends and a follow up call can be completed to address this request. For those who agree to participate, a letter summarizing the study and related activities and who to contact for questions will be mailed.

Therefore, the study team is asking for approval for telephone consent (Appendix III) and requesting a waiver of HIPAA from the IRB. All study staff have completed the required research training.

40.4 Explain how the research cannot practically be carried out without a waiver or alteration of informed consent.

As stated, the The CPCRS conducts the majority of their clinical care via telephone and do not have routine face-to-face contact with patients. CPCRS is located at Central Support Services which is not set up for in-person patient visits therefore we are asking for the alteration of informed consent.

40.5 Describe any plans you may have to provide pertinent information to the study participants at a later date (including any study findings/results). If the study is not designed to yield information that would be pertinent to the participants, please explain why.

We have no plans to provide study participants with information pertinent to the study at this time, however, if results are published, participants would have access to the results. Also, the results of this study may influence the care patients receive. Results will be shared/discussed with providers in aggregate form.

41.0 Informed Consent Questionnaire**41.1 Check the elements of informed consent that you wish to remove or alter. Provide an explanation in the associated text box. Check all that apply.**

- A statement that the study involves research.
-
- An explanation of the purpose of the research.
-
- The expected duration of the subject's participation.
-
- A description of the procedures to be followed.
-
- Identification of the procedures that are experimental.
-
- A description of any reasonably foreseeable risks or discomforts to the participant.
-
- A description of any benefits to the participant or to others that may reasonably be expected from the research.
-
- A disclosure of appropriate alternative procedures or courses of treatment, if any, that might be advantageous to the participant.
-
- A statement describing the extent, if any, to which confidentiality of records identifying the subject will be maintained.
-
- For research involving more than minimal risk, an explanation as to whether any compensation will be provided. Also an explanation as to whether any medical treatments will be provided if injury occurs, and if so, what kind, at whose expense, and where further information may be obtained.
-
- An explanation of whom to contact for answers to pertinent questions about the research participant's rights. Also whom to contact in the event of a research-related injury to the subject (standard statement, research questions, rights, injury).
- We provide this information in the study summary sheet mailed to all participants.
- A statement that participation is voluntary, refusal to participate in the study will involve no penalty or loss of benefits to which the participant is otherwise entitled, and the participant may discontinue participation at any time without penalty or loss of benefits to which the participant is otherwise entitled (standard statement).
-

